Primary Objective	Evaluate the efficacy of combined Vbeam PDL and topical RHOFADÉ cream (Arm 1) for improvement in erythematotelangiectatic rosacea at the 6-month follow-up compared to baseline and compared to RHOFADÉ treatment alone at the 6-month follow-up (Arm 2).
Secondary Objectives	
 • Evaluate the efficacy of combined Vbeam PDL and topical RHOFADÉ cream (Arm 1) for improvement in erythematotelangiectatic rosacea at each treatment visit (pre-treatments 2 and 3) compared to baseline. • Evaluate the efficacy of combined Vbeam PDL and topical RHOFADÉ cream (Arm 1) for improvement in erythematotelangiectatic rosacea compared to RHOFADÉ treatment only (Arm 2) at each study visit (pre-treatments 2 and 3 and 6-month follow-up for Arm 1 and at the 2-, 3-, and 6-month follow-up visits for Arm 2). • Both arms: Evaluate improvement in vessel size at each study visit (1, 2, 3 and 6 months post baseline visit). • Both arms: Evaluate subject satisfaction at each study visit (1, 2, 3 and 6 months post baseline visit). • Both arms: Evaluate overall improvement (investigator and subject) at each study visit (1, 2, 3 and 6 months post baseline visit).
Efficacy Endpoints	
 • Clinician erythema assessment (CEA) – Appendix II. • Subject self-assessment (SSA) 5-point scale – Appendix II. • Investigator and subject assessment, using a Global Aesthetic Improvement (GAI) 5-point scale – Appendix IV, Table 4. • Investigator assessment of Improvement in vessel size – Appendix IV, Table 5. • Subject satisfaction 5-point scale – Appendix IV, Table 6.
Safety Endpoints	
Evaluate the safety of the treatment (Arms 1 and 2):
 
 • Arm 1: Immediate treatment response – Appendix IV, Table 3. • Both Arms: Number, severity and type of any adverse event recorded throughout course of the study. • Arm 1: Discomfort level following PDL treatment – Appendix III.

BACKGROUND

Rosacea is a common chronic skin condition categorized into 4 subgroups based on clinical manifestations: erythematotelangiectatic, papulopustular, phymatous, and ocular [1]. Although the clinical features may

vary with rosacea, the most common primary feature of all subtypes is transient or persistent facial erythema [2,3]. Erythematotelangiectatic rosacea is primarily characterized by flushing and persistent central facial erythema [4].

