Early diagnosis and treatment based on subtype are recommended to halt progression of symptom severity [5]. Flushing is better prevented rather than treated, by avoiding specific triggers, decreasing transepidermal water loss by moisturizers, and blocking ultraviolet light [5]. Nonselective β -blockers and α 2-adrenergic agonists decrease erythema and flushing [5], while pulsed dye laser [5, 6] and intense pulsed light are used for telangiectasias [5]. Pulsed dye laser also addresses the diffuse erythema and enlarged pores characteristic of rosacea [6].

Oxymetazoline hydrochloride 1% cream (RHOFADE[™]) is a newly FDA-approved topical medication for adult rosacea patients. A primarily alpha-1a agonist, oxymetazoline hydrochloride (HCl) is thought to diminish erythema through vasoconstriction [7]. RHOFADE was evaluated for the treatment of persistent erythema associated with rosacea in two identical, randomized, double-blind, vehicle-controlled, parallel-group clinical trials [8]. A total of 489 subjects with persistent facial erythema associated with rosacea were treated with RHOFADE once daily for 4 weeks. An additional 440 subjects with persistent facial erythema associated with rosacea were also treated with RHOFADE once daily for up to one year in a long-term (open-label) clinical trial [8]. Disease severity was graded by the clinician using a 5-point clinician erythema assessment (CEA) scale [4] and by the subject on a similar 5-point subject self-assessment (SSA) scale, on which subjects scored either “moderate” or “severe” on both scales. Composite success, defined as the proportion of subjects achieving at least a 2-grade improvement on both CEA and SSA, was 15% in Trial 1 and 12% in Trial 2 on Day 29 of treatment [8].

Nonpurpuragenic pulsed dye laser (PDL) and intense pulsed light treatment have resulted in significant reduction in cutaneous erythema, telangiectasia and patient-reported associated symptoms of erythematotelangiectatic rosacea [9]. The PDL is an ideal energy-based device to treat the cutaneous vasculature of rosacea, since the 595nm wavelength is strongly taken up by the hemoglobin in blood vessels [6, 10]. With Vbeam 595nm PDL, ultra-long pulse durations reduce purpura while treating the telangiectasias associated with rosacea, which is more comfortable for patients [5, 6].

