A one-week post first PDL treatment safety follow-up visit will be conducted (1wk FU post Tx.1) for Arm 1 subjects. In addition, efficacy and safety evaluations will be performed at each study visit (1, 2, 3 and 6 months post-baseline visit), as shown in Figure 1 below..

Erythema severity will be assessed at baseline and at each study visit. Improvement in erythema severity will be assessed at each post baseline visit. Additionally, investigator and subject questionnaires will be completed. Photography will be performed at each study visit under visible light conditions of the front full face, right and left 45-degree profile and right and left 90-degree profile. VISIA photography may also be performed for spectrometry measurements (optional). Safety assessments will be conducted at each study visit.

Study Flowchart

Primary Efficacy Objective:

To evaluate the efficacy of combined Vbeam Prima PDL treatment and topical RHOFADÉ cream for improvement in erythematotelangiectatic rosacea, at the 6-month follow-up compared to baseline and compared to Arm 2 at the 6-month follow-up (RHOFADÉ drug therapy only).

Secondary Efficacy Objectives:

- Evaluate the efficacy of combined PDL and topical RHOFADÉ cream (Arm 1) for improvement in erythematotelangiectatic rosacea at each treatment visit (pre-treatments 2 and 3) compared to baseline.
- Evaluate the efficacy of combined PDL and topical RHOFADÉ cream (Arm 1) for improvement in erythematotelangiectatic rosacea compared to topical RHOFADÉ cream only (Arm 2) at each study visit (pre-treatments 2 and 3 and 6-month follow-up for Arm 1 and at the 2-, 3-, and 6-month follow-up visits for Arm 2).
- Evaluate subject satisfaction at each study visit (1, 2, 3 and 6 months post-baseline).
- Evaluate overall improvement (investigator and subject) at each study visit (1, 2, 3 and 6 months post-baseline).
- Evaluate improvement in vessel size (investigator) at each study visit (1, 2, 3 and 6 months post baseline visit).

Safety Objectives:

- Evaluate the safety of combined PDL treatment and topical RHOFADÉ cream (Arm 1) during the study.
- Evaluate comfort level associated with PDL treatment (Arm 1).

 Candela Corporation Confidential	Pilot Study to Evaluate Combined Vbeam[®] Pulsed Dye Laser Treatment and RHOFADE[™] (oxymetazoline hydrochloride) Topical Cream for Erythematotelangiectatic Rosacea			
	Protocol #	DHF24671	Rev. Date	June 11, 2018

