Comfort assessment will be performed independently by the subject using a numerical scale response (NSR) scale 0=No pain to 10=Worst possible pain (*Appendix III*). Subjects will be asked to fill out a questionnaire after each PDL treatment (Tx.1 – Tx.3).

Primary Efficacy Endpoint:

- Clinician erythema assessment (CEA): 5-point scale (0=Clear to 4=Severe) at 6-month follow-up compared to baseline.
- Subject self-assessment (SSA) 5-point scale similar to CEA at 6-month follow-up compared to baseline.

Secondary Efficacy Endpoints:

- Investigator and subject assessment of overall changes in skin condition (skin texture, vessel size, flushing), using a Global Aesthetic Improvement (GAI) 5-point scale (0=Excellent improvement to 4=No difference) – *Appendix IV, Table 4.*
- Investigator assessment of improvement in vessel size – *Appendix IV, Table 5.*
- Subject satisfaction 5-point scale (0=Very satisfied to 4=Very dissatisfied) – *Appendix IV, Table 6.*

Safety Endpoints:

- The number, severity and type of any adverse event recorded throughout the study and post-treatment (discomfort (pain), immediate and delayed response).
- Occurrence of expected post-treatment immediate response following each treatment based on a predefined scale (*Appendix IV, Table 3*).
- Discomfort (pain) level using a 10-point visual analog scale will also be recorded after each PDL treatment, using a Numerical Scale Response (NSR) – *Appendix III.*

Study Duration

The duration of the entire study from first subject enrollment to last subject completing the 6-month follow-up, is expected to be approximately 1 year.

Subject Population

Up to 60 healthy male and female adults (greater than 18 years of age), who meet the inclusion and exclusion criteria.

Subjects enrolled in the study can discontinue their participation at any time, for any reason, without prejudice or reduction in the quality of their medical care. In addition, the investigator or the sponsor can terminate a subject's participation in this study to protect the subject's health or if the subject is not compliant with the study protocol and schedule. Subjects may be replaced if withdrawn or lost from the study.

All subjects enrolled into this study must meet the following criteria:

Inclusion Criteria:

1. Subject is a healthy male or female of 18 to 75 years of age.

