The use of the device used in this clinical study has been determined to present a non-significant risk in accordance with 21 CFR 812.3 for the intended use in this study.

Potential benefits to participating individuals

Subjects may benefit by achieving visual improvement of their erythematotelangiectatic rosacea as a result of treatment in this study. Not all subjects may have complete clearance of their erythematotelangiectatic rosacea.

DATA ANALYSIS

Copies of Case Report Forms and photographs will be collected by the sponsor during the monitoring visit when appropriate and will be used for analysis of efficacy and safety.

Efficacy

The efficacy of combined Vbeam Prima PDL and topical RHOFADÉ cream for improvement in erythematotelangiectatic rosacea compared to baseline will be assessed by clinician erythema assessment, subject self-assessment, and Investigator and subject assessment, using a Global Aesthetic Improvement 5-point scale and subject satisfaction 5-point scale.

Safety

Safety of treatments will be evaluated throughout this study. Each treatment area will be evaluated for severity of purpura, edema, erythema, hyperpigmentation, hypopigmentation, blistering and scarring. All clinical response and complications observed either immediately following each treatment or at follow-up visits will be noted on the data forms. These data will be descriptively tabulated by treatment area.

Pain scores will also be assessed for safety.

Interim and Final Data Analysis

Interim analysis can be performed at any time and used to terminate the study should it seem necessary to do so.

 Candela Corporation Confidential	Pilot Study to Evaluate Combined Vbeam[®] Pulsed Dye Laser Treatment and RHOFADÉ™ (oxymetazoline hydrochloride) Topical Cream for Erythematotelangiectatic Rosacea			
	Protocol #	DHF24671	Rev. Date	June 11, 2018

ETHICS AND GOOD CLINICAL PRACTICE

This study will be carried out in compliance with the following:

- Syneron Candela Standard Operating Procedures.
- Declaration of Helsinki, concerning medical research in humans (Recommendations Guiding Physicians in Biomedical Research Involving Human Subjects, Helsinki 1964, amended Tokyo, 1975, Venice 1983, Hong Kong 1989, Seoul 2008 and Brazil 2013).
- US Code of Federal Regulations (Title 21CFR including parts 50, 56 and 812 governing informed consent and IRB regulations)

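### The primary result is undefined: the endpoint sets two scales against baseline, the objective adds a comparison between arms, and no rule joins them

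*Combined protocol and SAP*

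**What the plan says.** Four places in the combined protocol and SAP bear on the primary result.

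- **Study Design, Primary Efficacy Endpoint.** Under a singular heading there are two bullets: "Clinician erythema assessment (CEA): 5-point scale (0=Clear to 4=Severe) at 6-month follow-up compared to baseline" and "Subject self-assessment (SSA) 5-point scale similar to CEA at 6-month follow-up compared to baseline". Neither mentions Arm 2. Nothing says whether one scale or both must show a benefit, and no metric is given (mean change, grade shift or responder).
- **Primary objective (synopsis, and again in Study Design).** The combination is to be judged "at the 6-month follow-up compared to baseline and compared to" the cream-only arm. The comparison between arms enters the primary result only here.
- **Secondary objectives (both places).** Arm 1 is compared with Arm 2 at "pre-treatments 2 and 3 and 6-month follow-up for Arm 1 and at the 2-, 3-, and 6-month follow-up visits for Arm 2". The 6-month contrast is therefore both primary and secondary.
- **DATA ANALYSIS, Efficacy.** The efficacy of the combination "for improvement in erythematotelangiectatic rosacea compared to baseline will be assessed by clinician erythema assessment, subject self-assessment", followed by the GAI and satisfaction scales in the same sentence. Arm 2 is not mentioned. No test, significance level, success criterion or order of testing is given.

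The Background describes a joint rule used in the cited drug trials: "Composite success, defined as the proportion of subjects achieving at least a 2-grade improvement on both CEA and SSA, was 15% in Trial 1". This study does not adopt it.

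**The concern.** The two comparisons in the primary objective answer different questions. Arm 1 against its own baseline shows whether subjects on cream plus laser got better. Arm 1 against Arm 2 at 6 months shows whether adding the laser course to the cream made a difference, and it is the only comparison that uses the randomization.

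Arm 1 can be expected to improve on baseline even if the laser does nothing, for two reasons found in the plan itself. First, both arms apply a cream that the protocol describes as approved for this condition. Second, inclusion criterion 2 requires grade 3 or 4 on both CEA and SSA, and Table 2 has a single screening/baseline column, so the qualifying score is also the baseline score. Selecting subjects on a high score builds in some regression to the mean.

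An analyst who follows the endpoint and DATA ANALYSIS sections would treat the baseline comparison as primary. One who follows the objective would also need the comparison between arms. If the first is positive and the second is not, the plan does not say what the trial found. The same gap opens if CEA and SSA disagree. That is plausible, because one is clinician-rated and the other subject-rated, no blinding is described, and only Arm 1 receives the laser.

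**Working it through.** The plan states no figure to reproduce: there is no significance level, power, effect size or SD behind the sample size.

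**Inputs.** From the documents: up to 60 subjects, two arms, two scales scored 0 to 4, and two comparisons at 6 months. Assumed: 1:1 allocation (30 per arm; the ratio is not stated), two-sided 5% per test, and a normal approximation for the mean change.

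**1. How often the baseline test succeeds when the laser adds nothing.** Let both arms improve by the same d SD of change. The chance that Arm 1's test against baseline is significant is Φ(d√n − 1.960).

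| d | n = 30 | n = 20 |
|---|---|---|
| 0.5 | Φ(2.739 − 1.960) = 78% | Φ(2.236 − 1.960) = 61% |
| 0.75 | Φ(4.108 − 1.960) = 98% | Φ(3.354 − 1.960) = 92% |
| 1.0 | Φ(5.477 − 1.960) = over 99.9% | Φ(4.472 − 1.960) = 99% |

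With a t test on 29 degrees of freedom, the n = 30 values are 75%, 98% and over 99.9%. The n = 20 column shows the effect of fewer evaluable subjects. In every row the between-arm test stays at 5%, because a shared improvement cancels in the difference.

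**2. Either scale allowed to succeed, between arms.** This is illustration only, since the plan sets no level. With no true difference on either scale, the chance of at least one significant result is 1 − 0.95² = 9.75% if the scales are uncorrelated. It is 9.1% at correlation 0.5 and 7.0% at 0.9.

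**3. Any of the four results allowed to succeed.** This is also illustration only, with no change in either arm. Two scales by two comparisons give four tests. On one scale the two tests share Arm 1's data: with z_within = a and z_between = (a − b)/√2, their correlation is 1/√2 = 0.71. Simulation with that structure gives 15.9% at CEA–SSA correlation 0, then 14.8% at 0.5, 13.6% at 0.7 and 11.6% at 0.9. The independent-tests value, 1 − 0.95⁴ = 18.5%, cannot occur here.

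Step 1 carries the point. Steps 2 and 3 only show the price of leaving the rule open.

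**The case against.** The study calls itself a baseline-controlled pilot. It promises assessment of change, not a confirmatory test, and a pilot need not control error strictly. The primary objective joins its two comparisons with the word and, which can be read as requiring both. These points have weight. They soften the need for a formal error budget, but they do not settle which comparison is the main result. The study is randomized, and the endpoint and analysis sections leave out the contrast for which randomization is needed.

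A reader might infer more than the documents support:

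- **That the false-positive rate exceeds the plan's nominal 5%.** The plan sets no level, so the 7% to 16% figures are not corrections of anything stated. A significant baseline result would usually not be a false positive either. Improvement is expected, so the finding would be true but would answer another question.
- **That success may be claimed on whichever result is favourable.** The text does not say this. It also does not exclude it.
- **That every secondary rating at every visit is a further between-arm test.** Only one secondary objective compares the arms, at 2, 3 and 6 months. Overall improvement, vessel size and satisfaction are to be evaluated, with no comparison between arms named. The month-1 ratings also precede the first laser treatment.
- **That listing the 6-month contrast twice raises the error rate.** It is one test on one set of data, so the repetition is only a conflict of labels.

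**Conclusion.** The concern holds as a problem of definition. The endpoint, the objectives and the analysis section disagree on what the primary comparison is, and no rule covers disagreement between CEA and SSA. The practical consequence is that a primary result could be declared positive on the baseline comparison when the laser adds nothing. That happens with probability of roughly 75% to over 99.9% on one scale if both arms improve by 0.5 to 1.0 SD of change. This rests on 30 evaluable subjects in Arm 1 and a two-sided 5% test; with 20 subjects the range starts at about 61%. The size of the shared improvement is an assumption, but its direction follows from the plan's own design. The conclusion does not depend on the multiplicity figures. The plan should be corrected before any outcome data are seen.

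**What to change.** 1. State in the objectives, in the endpoint section and in DATA ANALYSIS that the primary comparison is Arm 1 versus Arm 2 at 6 months in change from baseline.
2. Name the metric for CEA and SSA, for example mean change or the proportion improving by a stated number of grades.
3. Fix one decision rule for the two scales before any data are seen. Two valid options are CEA first and then SSA in fixed sequence at two-sided 5%, or both scales required. Neither needs the level to be split. Requiring both is conservative: the chance that both are significant when neither differs is 0.25% to 3.0% for correlation 0 to 0.9.
4. Report Arm 1 against baseline, and all other scales and visits, as estimates with 95% confidence intervals.
5. Delete the 6-month visit from the secondary between-arm objective.

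The change is to wording only; it adds no visits or subjects. It has two costs. Improvement from baseline, or SSA alone, can no longer carry the efficacy conclusion. The comparison between arms is also more demanding: with 30 per arm, 80% power at two-sided 5% needs a difference of (1.960 + 0.842) × √(2/30) = 0.72 SD. The study may therefore yield an estimate with a wide interval, which is acceptable for a pilot if stated in advance.

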Inclusion/ Exclusion Criteria	X				
Subject # Assignment	X				
Randomization to Study Arm	X				
Pregnancy Urine test	X				
Vbeam PDL test spots, (optional) – Arm 1	X	X		X	
Change to Medical History		X	X	X	X
Photographs, prior to any treatments		X	X	X	X
VISIA photographs, prior to any treatments (optional)		X	X	X	X
Clinician erythema assessment (CEA), prior to any treatments	X	X		X	X
Subject self-assessment (SSA), prior to any treatments	X	X		X	X
Vbeam PDL Treatment – Arm 1		X		X	
Tx Pain Assessment – Arm 1		X		X	
Immediate Treatment Response – Arm 1		X		X	

Visit	Screening /Baseline	Tx 1*/ 1-month FU	1-week (± 2 days) Safety Evaluation	Tx 2 - 3 / 2 & 3-Month FU Visits (4± 1 week)	6-Month (± 2 weeks) FU
Photographs, 10 mins post any treatment (optional) – Arm 1		X		X	
Global Aesthetic Improvement (GAI)		X		X	X
Vessel size assessment		X		X	X
Subject Satisfaction Questionnaire		X		X	X
Adverse Events and Serious Adverse Events	X	X	X	X	X
End of participation (Termination)					X

*For Arm 1, the 1st PDL treatment will be scheduled at approximately 4 weeks following the screening visit.

Screening Procedures

- A brief relevant medical history will be obtained to address inclusion/exclusion criteria for the study.
- Clinician erythema assessment (CEA) and subject self-assessment (SSA) will be obtained to address inclusion criteria for the study. Subjects with “moderate” or “severe” (Grade 3 or 4) are eligible for study participation (*Appendix II*).
- Pregnancy will be assessed for female subjects based on their last menstrual period, ability to become pregnant (surgical sterilization, birth control), and whether they have plans to become pregnant during the 6-month study period.
- The subject will undergo a standard skin exam to determine if they meet the study criteria.
- If the subject meets the criteria for the study, he or she will discuss with the study staff the study procedures, risks, benefits, and commitments associated with enrollment into the study. The staff will then review the consent form in detail with the subject, after which the subject will be given ample time to review the form. The subject will sign a consent form after the subject fully understands the possible risks/benefits of the study and wants to participate in study. The person conducting the session and the investigator will subsequently sign the consent form.

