APPENDIX I – Photography Guidelines

At each time point (before the treatments and at the follow-up visits), photographs of the treated facial areas should be taken in a standardized manner.

- Photographs should be taken in a private room or area of the clinic under controlled conditions, including the distance from the camera to the subject, height of the camera, background, camera positioning, subject's positioning and lighting in order to achieve high quality before & after sets.
- For consistency purposes, the same person should ideally take all study photographs, especially per subject.
- Subject's hair should be pulled away from the face with a hairband or shower cap.
- The digital files should follow a consistent standard naming scheme (including: date, subject study ID, subject initials, for example: 001TS_Tx.1_Mar 21 2015, etc.).

Specific photography details for facial area:

- Front face
- 90° right profile and left profile
- 45° right profile and left profile

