Appendix IV – Assessment scales

Table 3 – Post-treatment Side Effect Severity Scale

(0) Absent / None	
(1) Mild	
(2) Moderate	
(3) Severe	

Table 4 – Global Aesthetic Improvement (GAI) Scale

(0) Excellent improvement	
(1) Good improvement	
(2) Moderate improvement	
(3) Slight improvement	
(4) No change	

Table 5 – Improvement in Vessel Size

(0) 76–100% improvement (excellent)	
(1) 51–75% improvement (marked)	
(2) 26–50% improvement (moderate)	
(3) 1–25% improvement (mild)	
(4) No response	

Table 6 – Satisfaction Scale

(0) Very Satisfied	
(1) Satisfied	
(2) No Opinion	
(3) Dissatisfied	
(4) Very Dissatisfied	

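### No baseline photograph is scheduled although later sections presume one; as a minor point, the GAI and vessel-size scales have no grade for worsening

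*Combined protocol and SAP*

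**What the plan says.** **Photographs.** In Table 2 (Study Schematics) the row "Photographs, prior to any treatments" and the optional VISIA row are blank under Screening/Baseline; the first mark is at Tx 1 / 1-month. Screening Procedures lists no photograph. Appendix I gives the timing as "At each time point (before the treatments and at the follow-up visits), photographs of the treated facial areas should be taken", with no screening or baseline time point. Follow-up Study Visits, however, says that photography and VISIA repeat what was done at the baseline visit, and the Photographs section says the images are used for the investigator and subject assessments.

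**Scales.** Secondary Efficacy Endpoints describes the GAI as an "assessment of overall changes in skin condition (skin texture, vessel size, flushing" and so on, scored "using a Global Aesthetic Improvement (GAI) 5-point scale (0=Excellent improvement to 4=No difference". Appendix IV Table 4 has four grades of improvement, then one for no change. Table 5 (vessel size) has four bins of improvement, then one for no response. Table 6 (satisfaction) does have a negative side, down to "4) Very Dissatisfied".

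**Comparator.** Data Analysis, Efficacy, says that the combination "compared to baseline will be assessed by clinician erythema assessment, subject self-assessment, and Investigator and subject assessment, using a Global Aesthetic Improvement 5-point scale". Vessel size is not in that list, though baseline can be inferred for it.

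**The concern.** GAI and vessel size are ratings of change, and Table 2 gives neither of them a score at Screening/Baseline. The rater needs something to compare with, and a photograph is the natural record. If the earliest image is taken after weeks of a vasoconstrictor cream, a comparison with baseline rests on recall, or on an image in which the two arms are in different drug states. An image missed before the first application cannot be made later.

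The scale issue is separate and smaller. A scale said to rate changes but offering only improvement or none cannot show deterioration. What is at stake is how faithfully two secondary endpoints of a pilot are recorded.

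**Working it through.** **A. Photographs: the text set side by side**

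Marks in Table 2, by column:

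| Row | Screening/Baseline | Tx 1 / 1-month | 1-week | Tx 2–3 / 2 & 3-month | 6-month |
|---|---|---|---|---|---|
| Photographs; VISIA (optional) | blank | X | X | X | X |
| CEA; SSA | X | X | blank | X | X |
| GAI; vessel size | blank | X | blank | X | X |

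1. A cell lost in reading the PDF is unlikely. The CEA and SSA rows keep their Screening/Baseline mark, and the 1-week mark for photographs agrees with the 1-week visit list in the text.
2. Study Design has both arms receive the cream at the screening visit. The footnote to Table 2 puts the first laser treatment about 4 weeks after screening. The first scheduled image therefore follows about 4 weeks of cream.
3. At that visit Arm 1 is in the washout required before each laser treatment, while Arm 2 has been told to use the cream without interruption to month 6.
4. The rows for GAI and "Vessel size assessment" have their first mark at the same visit. The first change scores and the first image coincide.
5. Study Design and the Photographs section call for photographs at each study visit. Study Design gives those visits as 1, 2, 3 and 6 months after baseline and, for erythema severity, names baseline in addition to each study visit. Study Procedures, on the other hand, introduces Table 2 as a summary of the required study visits, and its first column is Screening/Baseline. The two usages differ, so the phrase does not settle the matter.

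**B. Scales: size of the effect**

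Inputs: grades from Appendix IV Tables 4 and 5; up to 60 subjects (Study Design); an even split of 30 per arm, which is assumed because no allocation ratio is stated. The documents give no worsening rate for either scale. The nearest figure is 3% over one year for worsening inflammatory lesions on the cream (Study Drug), a different outcome used here only as a proxy.

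Score improvement as 4 minus the grade, so the last grade counts 0 and an added grade 5 counts −1. Let *w* be the proportion of an arm that worsens, all recorded in grade 4 as the scale stands.

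- *Mean improvement.* Each worsened subject moves from 0 to −1, so the arm mean falls by *w* × 1 = *w*. At 3% that is 0.03 category, and 30 × 0.03 = 0.9, about 1 subject per arm. At an arbitrary 10% it would be 0.10 category and 30 × 0.10 = 3 subjects.
- *Difference between arms.* It changes by *w*₁ − *w*₂: nothing if the rates are equal, 0.03 for 3% versus 0%, 0.10 for 10% versus 0%.
- *Responder rate* (proportion reaching a stated improvement grade, 0 to 3). Grades 4 and 5 are both non-response, so the change is 0.

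These results need no assumption about the distribution of the scores. They do assume that worsened subjects are recorded in the last grade. If they were left blank and dropped from the denominator, a responder rate would be inflated by 1/(1 − *w*), which is 1/0.97 = 1.03 at 3%.

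**The case against.** **On photographs.** Since Study Procedures treats every column of Table 2 as a study visit, the instruction to photograph at each study visit may already cover baseline, and Follow-up Study Visits plainly takes it for granted. The likeliest explanation is one missing mark and one omitted list item. That stands as a reading of intent. It does not help a site that works from the schedule, and Screening Procedures and Appendix I are silent in the same place. A reader might infer that the trial has no baseline photograph; the documents support only that its sections disagree.

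**On the scales.** The objectives speak of improvement, and so do the titles of Tables 4 and 5, so a scale that stops at no change is a defensible choice; only the description of the GAI as rating changes points the other way. Worsening is also partly caught elsewhere. CEA and SSA are absolute scales with a baseline score, satisfaction has negative grades, and adverse events are collected at every visit. This stands, and it is why the scale issue is minor. The cover is incomplete: subjects enter CEA and SSA at grade 3 or 4 of a scale that ends at 4; one of the two adverse event definitions is confined to events related to the device or study procedures; and none of these measures grades vessel size or skin texture.

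**On the size.** Data Analysis names no mean, test or other summary for the GAI and does not mention vessel size, so a shift in means is conditional on grades being averaged. That stands too. A reader might go on to infer that the missing grade biases the arm comparison in a known direction, or by a sizeable amount. The documents do not support this: they give no worsening rate by arm and no standard deviation for either scale.

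**Conclusion.** The photograph point holds as an internal inconsistency that should be resolved. Three places that should schedule a baseline image do not, while later text relies on one. The consequence for a site following Table 2 cannot be repaired afterwards, and it leaves the earliest image in a different drug state in each arm.

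The scale point holds as a minor one. Neither scale has a worsening grade, and the GAI is said to rate changes. No rule says that a worsened subject must be scored as unchanged; that is the likely outcome, with a blank as the alternative. If grades are averaged, the effect equals the proportion who worsen, about 0.03 category or 1 subject in 30 at the proxy rate of 3%, assuming an even split. If a responder proportion is reported and worsened subjects stay in the denominator, there is no effect.

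A reader might infer that the primary endpoint is undermined. Table 2 has CEA and SSA scored at Screening/Baseline, so it does not depend on either gap.

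**What to change.** **Photographs.** Mark photographs, and VISIA where used, at Screening/Baseline in Table 2. List them in Screening Procedures and Appendix I, taken before the first cream application. State in Data Analysis that GAI and vessel size are scored against that baseline in both arms. No baseline vessel-size score is needed, because Table 5 already grades change.

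**Scales.** Add a grade (5) *Worse* to Tables 4 and 5. Then amend the number of points given for the GAI in the synopsis ("Investigator and subject assessment, using a Global Aesthetic Improvement (GAI) 5-point scale"), in Secondary Efficacy Endpoints and in Data Analysis. Bring the end label in Secondary Efficacy Endpoints into line with Table 4, which words it differently.

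**Cost.** Small edits to tables and case report forms, and one photograph set at an existing visit, which the follow-up text already presumes. Reported mean improvement may come out slightly lower.
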